9.8 Study Restrictions

9.8.1 Food and Fluids

No food will be allowed from at least 10 hours before dosing until at least 4 hours after dosing with the exception of one piece of candy for each subject after each dosing due to the bitter taste of the study drug.

Subjects will be in a fasting state before safety laboratory assessments including hematology, biochemistry, coagulation (PT and PTT) and urinalysis.

Meals will be standardized and similar in composition between periods.

Except for water given with study medication, no fluids will be allowed for 1 hour before dosing until 1 hour post-dose. Water will be provided *ad libitum* at all other times.

In addition, subjects will be required to abstain from:

- Food containing poppy seeds within 24 hours prior to admission of each period;
- Food or beverages containing xanthine derivatives or xanthine-related compounds or energy drinks from 48 hours pre-dose (for subjects who regularly consume large amounts i.e. ≥ 5 cups of coffee/day the restriction will be from one week pre-dose) until after the last PK blood sample collection of each period;
- Natural health products (including herbal remedies, homeopathic and traditional medicines, probiotics, food supplements such as vitamins, minerals, amino acids, essential fatty acids, and protein supplements used in sports) from 7 days prior to first dosing until study exit;

- St John's wort and any drugs known to induce or inhibit hepatic drug metabolism from 30 days prior to first dosing until study exit;
- Food or beverages containing grapefruit, starfruit, pomegranate, pineapple, or pomelo from 7 days prior to dosing until after the last pharmacokinetic blood sample collection of each period.

9.8.2 Tobacco, Alcohol, and Illicit Drugs

Subjects will be required to abstain from using soft or hard drugs or any tobacco or nicotine products from screening until study exit.

Consumption of alcohol-based products will be prohibited from 24 hours prior to admission until after the last pharmacokinetic blood sample collection of each period.

9.8.3 Concomitant Medications

Subjects will be required to avoid using prescription and OTC medications, and depot injections or implant of any drug for the period of time specified in exclusion criterion 18) until study exit. No concomitant drug therapy will be allowed during the study except one(s) required for the medical management of an adverse event. Any concomitant medication use other than the occasional use of acetaminophen (up to 2 g daily) will be evaluated on a case-by-case basis by the Investigator or a Sub-investigator. All concomitant medication use will be documented from screening through study exit/early termination.

9.8.4 Posture and Physical Activity

Subjects will be required to remain in a supine or semi-reclined position but avoid sleeping for the first 4 hours after study treatment administration. However, failure of subjects to comply with these requirements does not constitute a deviation from the protocol if it is medically necessary, required for procedures, or to go to the bathroom. When appropriate, subjects will be accompanied by a staff member while walking. Vigorous activity will be prohibited at all times during the confinement.

9.8.5 Other Restrictions

During the period for which subjects are wearing a Holter monitor, access to laptop, iPod, cell phone, books or TV will be restricted and controlled. In addition, female participants will be required to either remove their bra if any, or wear a bra with no underwire, such as sports bra. If female participants prefer not to wear a bra, it will need to be removed before the placement of electrodes for the continuous recording of their heart rhythm. In both cases, if participant chooses not to wear a bra or wear a wireless bra, it must be for the duration of the entire recording.

9.9 Sample Collection and Processing

During the study, all samples will be collected and processed according to the vendor-specific SOP. At the end of the study and after study report elaboration, samples obtained for clinical laboratory assessments and for PK analysis will be destroyed.

9.9.1 Blood Samples

In each period a total of 19 blood samples will be drawn from each subject for PK analyses. Blood samples for the measurement of ITF2357 and metabolites: ITF2374, ITF2375, ITF2440, ITF2563, ITF2955 glucuronide, and moxifoxacin will be collected. Only samples from subjects who receive ITF2357 and moxifloxacin will be analyzed, samples from subjects who receive placebo will be saved for analysis if needed.

Samples will be collected pre-dose and 0.5, 1, 1.5, 2, 2.5, 3, 3.5, 4, 5, 6, 7, 8, 12, 24, 36, 48, 60 and 72 hours post-dose (6 mL for each sampling time for study treatments S, ST, and P; 3 mL for study treatment M).

ITF2357 will be quantified in all subjects administered with the study drug while the metabolites will be quantified only in a randomized group of 12 subjects, as no effect from the metabolites is expected on the QTc results. The samples that would not be analyzed will be kept frozen until bioanalysis results are obtained, if within these results any indication of a possible effect is found, all samples would be further studied. Blood draws will be performed after the 15-minute supinely resting period around each time point for ECG extraction. The time tolerance window for blood samples collected during the confinement period will be ± 10 minutes for all samples. Sample collections done outside the pre-defined time windows will not be considered as protocol deviations since actual post-dose sampling times will be used for pharmacokinetic and statistical analyses. A dead-volume intravenous catheter will be used for blood collection to avoid multiple skin punctures, when appropriate. Otherwise, blood samples will be collected by direct venipuncture.

The total volume of blood including that collected for eligibility and safety purposes should not exceed 435 mL for the whole study.

Before starting bioanalysis, the biostatistician will randomly select 12 evaluable subjects for plasma metabolite analysis. These will be the same 12 evaluable subjects randomely selected for urinary metabolte analysis.

Plasma samples will be collected and processed as per the Analytical Methodology Information Sheet (AMIS).

9.9.2 Urine Sample Collection

During treatment with T, ST, and P, urine will be collected from each subject at 5 times or time intervals: spot pre-dose (within 2 hours before dosing), 0-8 hours, 8-24 hours, 24-48 hours, and 48-72 hours post-dose.

Urine samples will be collected from all subjects, but only urine samples from 12 randomized subjects will be used for the PK analyses of ITF2357 and metabolites: ITF2374, ITF2375, ITF2440, ITF2563, and ITF2955 glucuronide. The rest of the samples will be kept frozen for further analysis in case any indication is found of a possible effect of the metabolites on the QTc analysis.

If a subject cannot void his or her bladder within 30 minutes before dosing, a sample from earlier that morning may be used as the pre-dose sample. Voids that occur within the time interval will

be pooled, and subjects will be asked to void their bladder within 30 minutes before the end of each collection interval, so that each new interval will begin with an empty bladder. Any urine voided by subjects at the intersection (within 10 minutes) of two intervals will be included in the earlier sample. Any urine voided by subjects but not collected will be documented.

Before starting bioanalysis, the biostatistician will randomly select 12 evaluble subjects for urinary metabolite analysis. These will be the same evaluable subjects randomely selected for plasma metabolte analysis.

Urine samples will be collected and processed as per the AMIS.

9.10 Subject Monitoring

Subjects will be monitored throughout the study by the clinical staff for AEs. In each period, an Ivestigator or Sub-investigator will be on site for drug administration and until 4 hours post-dose, and available on call for the remainder of the study. If necessary, an Investigator or designee, at the clinical site or a healthcare professional in a nearby hospital will administer treatment for any adverse event(s). A crash cart or emergency bag containing the necessary rescue material and appropriate medications will be available in the clinic to allow rapid intervention in case of emergency.

Safety parameters, including laboratory results and ECG, will be assessed by an Investigator or Sub-investigator, using the clinical site's criteria for biomedical laboratory and ECG acceptance ranges as suggested guidelines in making the medical assessment.

Scheduled safety measurements will be repeated according to the clinical site SOPs or upon request from an Investigator or Sub-investigator. Any abnormal repeated measurement will be evaluated by an Investigator or Sub-investigator and repeated if judged necessary. Further action may be taken upon an Investigator or Sub-investigator's request.

Subjects will be advised to notify their health care professional(s) (e.g., physician, dentist, and/or pharmacist) that they are participating in a clinical research study on a drug called ITF2357 (Givinostat), which is being developed by Italfarmaco S.p.A. for potential clinical use in patients suffering from Muscular Dystrophies including Duchenne and Becker Muscular Dystrophy, and chronic myeloproliferative neoplasms including Polycythemia Vera, before taking any medicines or undergoing any medical procedure.

9.10.1 Vital Signs

BP, HR, RR, and OT will be measured in a supine position at: screening, pre-dose and approximately 2, 3, 6, 12 and 24 hours post-dose for each period, and at study exit. Vital signs will be matched to the safety ECG (at screening, pre-dose and approximately 2, 3, 6, 12, and 24 hours post-dose for each period, and at study exit). When vital signs measurements coincide with ECG or blood draw, the assessments will be performed in the following order: ECG, vital signs, and blood draw. Urine collection timepoints will not be prioritized over safety and other PK assessments.

For the measurement of BP, two measures performed after at least 5 minutes of resting in supine position should be taken 2 minutes apart from each other.

9.10.2 Safety ECG

Supine 12-lead ECG will be performed at screening, pre-dose and approximately 2, 3, 6, 12 and 24 hours post-dose for each period, and at study exit. Safety ECG will be matched to vital signs (at screening, pre-dose and 2, 3, 6, 12 and 24 hours post-dose for each period, and at study exit). When ECG coincides with vital signs measurements or blood draw, the assessments will be performed in the following order: ECG, vital signs, and blood draw. Urine collection timepoints will not be priortized over safety and other PK assessments.

9.10.3 Continuous ECG Recording

The cardiodynamic assessment will be performed through 12-lead ECGs extracted from continuous recordings at pre-specified time points, paired with PK samples.

Continuous 12-lead ECG recordings will be performed from one hour prior to dosing in each treatment period to 36 hours post-dose. The 12-lead Holter and ECG equipment will be supplied and supported by ERT. All ECG data will be collected using Global Instrumentation (Manlius, NY, USA) M12R ECG continuous 12-lead digital recorder. The continuous 12-lead digital ECG data will be stored onto SD memory cards. 12-lead ECGs will be extracted from the continuous recordings at pre-determined time points as defined in Section 4. Schedule of Events, and will be measured centrally by ERT.

Subjects will be supinely resting for at least 10 minutes prior to and 5 minutes after each time point for ECG extractions, whenever possible. Subjects will be required to avoid postural changes during these ECG recordings.

When time points for ECG extractions coincide with vital signs measurements, and blood draws, procedures will be carried out in that order. Urine collection timepoints will not be priortized over safety and other PK assessments.

At the ECG core laboratory, up to 10 replicate ECGs will be extracted at each of the following time points on Day 1 in each treatment period: 3 time points prior to dosing (-45, -30 and - 15 minutes) and 0.5, 1, 1.5, 2, 2.5, 3, 3.5, 4, 5, 6, 7, 8, 12, 24, and 36 hours post-dose. The following principals will be followed in ERT's core laboratory:

- ECG analysts are blinded to the subject, visit and treatment allocation
- Baseline and on-treatment ECGs for a particular subject will be over-read on the same lead and will be analyzed by the same reader
- The primary analysis lead is lead II. If lead II is not analyzable, then primary lead of analysis will be changed to another lead for the entire subject data set.

The following is a brief description of ECG analysis methods utilized by ERT's core laboratory.

9.10.3.1 TQT Plus ECG Extraction Technique

Ten 14-second digital 12-lead ECG tracings will be extracted from the continuous Holter recordings using the 'TQT Plus method', a computer-assisted and statistical process utilized by ERT. The method enables extraction of ECGs with the lowest HR variability and noise within the protocol-specified extraction time window (e.g., the HR and QT changes from beat-to-beat in the range of <10%). At each protocol-specified timepoint, 10 ECG replicates will be extracted from a 5-minute "ECG window" (typically, the last 5 minutes of the 15-minute period when the subject is maintained in a supine or semi-recumbent quiet position).

9.10.3.2 Expert-Precision QT Analysis

Expert-precision QT analysis will be performed on all analyzable (non-artifact) beats in the 10 ECG replicates. Statistical quality control procedures are used to review and assess all beats and identify "high" and "low" confidence beats using several criteria, including:

- QT or QTc values exceeding or below certain thresholds (biologically unlikely).
- RR values exceeding or below certain thresholds (biologically unlikely).
- Rapid changes in QT, QTc or RR from beat to beat.

Measurements of all primary ECG parameters (QT, QTc, RR) in all recorded beats of all replicates that are deemed "high confidence" is performed using COMPAS software. All low confidence beats are reviewed manually and adjudicated using pass-fail criteria. The final QC assessment is performed by a cardiologist. The beats found acceptable by manual review are included in the analysis. The median QT, QTc, and RR value from each extracted replicate is calculated, and then the mean of all available medians from a nominal timepoint is used as the subject's reportable value at that timepoint.

Categorical T-wave morphology analysis and the measurement of PR and QRS intervals will be performed manually in 3 of the 10 ECG replicates at each timepoint. Each fiducial point (onset of P-wave, onset of Q-wave, offset of S-wave, and offset of T-wave) is electronically marked.

For T-wave morphology and U-wave presence, treatment-emergent changes will be assessed, i.e., changes not present at baseline. For each category of T-wave morphology and of U-waves, the category will be deemed as present if observed in any replicates at the time point. For baseline, the category will be deemed as present if observed in any replicates from all time points that constitute baseline. The T-wave morphology categories are described as follows.

Table 1: T-wave morphology and U-wave presence categories (assessed manually)

Category	Description
Normal T-wave	Any positive T-wave not meeting any criterion below
Flat T-wave	T amplitude < 1 mm (either positive or negative) including flat isoelectric line
Notched T-wave (+)	Presence of notch(es) of at least 0.05 mV amplitude on ascending or descending arm of the positive T-wave

Category	Description
Biphasic	T-wave that contains a second component with an opposite phase that is at least 0.1 mV deep (both positive/negative and negative/positive and polyphasic T-waves included)
Normal T-wave (-)	T amplitude that is negative, without biphasic T-wave or notches
Notched T-wave (-)	Presence of notch(es) of at least 0.05 mV amplitude on descending or ascending arm of the negative T-wave
U-waves	Presence of abnormal U-waves

9.10.4 Physical Examination

A complete physical examination will be performed at screening and at study exit. A complete physical examination includes assessments of the following: head, eyes, ears, nose, throat (HEENT), neck (including thyroid), chest, lungs, abdomen, back, lymph nodes, musculoskeletal, dermatological, cardiovascular/peripheral vascular, and general neurological examination.

In Periods 1, 2 and 3, a brief physical examination will be performed at check-in on Day -1, and approximately 24 and 72 (Day 4) hours post-dose. In Period 4, a brief physical examination will be performed at check-in on Day -1 and approximately 24 hours post-dose. A brief physical examination includes assessments of the following: HEENT, chest, lungs, abdomen, dermatological, cardiovascular/peripheral vascular, and areas of note elicited from the subject.

Body measurements including body height, body weight and BMI will be measured at screening. Body weight will be measured at check-in (Day -1) for each period.

9.10.5 Drug, Alcohol, and Cotinine Screen

A urine drug screen (amphetamines, methamphetamines, barbiturates, benzodiazepines, tetrahydrocannabinol, cocaine, opiates, PCP, MDMA, methadone), an alcohol breath test, and a urine cotinine test, will be performed at screening. A urine drug screen, an alcohol breath test, and a urine cotinine test and will also be performed before dosing of each period.

9.10.6 Pregnancy Test

A urine pregnancy test will be performed at screening and at study exit, and a serum pregnancy test will be performed at check-in of each period.

9.10.7 Laboratory Assessments

9.10.7.1 Hematology

Fasting hematology will be performed at screening, before dosing of each period (at check-in or in the morning of Day -1), 24 (Day 2) and 72 (Day 4) hours post-dose, and at study exit. The following will be assessed: complete blood count with differential, hemoglobin, and hematocrit.

9.10.7.2 Biochemistry

Fasting biochemistry will be performed at screening, before dosing of each period (at check-in or in the morning of Day -1), 24 (Day 2) and 72 (Day 4) hours post-dose, and at study exit. The following will be assessed: cholesterol [total, LDL and HDL], triglycerides, albumin, alkaline phosphatase, AST, ALT, urea, cystatin C, calcium, chloride, glucose, phosphorus, potassium, creatinine, sodium, total bilirubin, and total protein.

9.10.8 Coagulation

Fasting coagulation will be performed at screening, before dosing of each period (at check-in or in the morning of Day -1), 24 (Day 2) and 72 (Day 4) hours post-dose, and at study exit. The following will be assessed: PT and PTT.

9.10.8.1 Serology

Serology will be performed at screening. The following will be assessed: HIV antigen and antibody, hepatitis B surface antigen (HBsAg), and hepatitis C virus (HCV) antibody.

9.10.8.2 Urinalysis

Fasting urinalysis will be performed at screening and before dosing of each period (at check-in or in the morning of Day -1), 24 and 72 hours post-dose, and at study exit. The following will be assessed: macroscopic examination, pH, specific gravity, protein, glucose, ketones, bilirubin, occult blood, nitrite, urobilinogen, and leukocytes. Unless otherwise specified, microscopic examination will be performed on abnormal findings.

9.11 Study Exit Procedures (End of Trial Visit/Early Termination Visit)

This visit is performed at the end of the subject participation in the trial, upon completion on Day 4 of Period 4. Study procedures performed on Day 4 of Period 4 will serve as study exit procedures. This visit is also performed in case of early termination or withdrawals, in this case, study procedures will be done the same day of withdrawal or as soon as possible but always within 14 days after last participation of the subject in the study. If clinically significant abnormal results are found on the laboratory assessments performed during Study Exit/Early Termination, the subject will be invited to the site clinic again to repeat abnormal parameters.

The following procedures should be performed: complete physical examination, fasting safety laboratory assessments including hematology, biochemistry, coagulation (PT and PTT), and urinalysis, supine vital signs [BP, HR, RR and OT], 12-lead ECG, urine pregnancy test, AEs monitoring, and concomitant medications.

9.12 Follow-up Telephone Call (Day 12±2 days):

A follow-up telephone call will be made to all subjects to monitor ongoing AEs or to check for possible AEs on Day 12±2 days after dosing in Period 4.

9.13 Data Collection and Evaluation

Subjects' personal information will be stored in an electronic data capture (EDC) system (InitiatorTM or Alphadas[®]). All clinical raw data will be recorded promptly, accurately, and legibly, either directly into the EDC system as e-source data or indelibly on paper (e.g., raw data sheets when electronic data capture is not possible). A detailed list of the type (electronic or paper) and location for all source data will be included in the Trial Master File. When recorded electronically, Case Report Forms will be electronically generated afterwards. All raw data will be conserved in order to maintain data integrity. The Qualified Investigator and designee have the responsibility of ensuring the completeness and accuracy of the clinical data.

All laboratory results provided by Biron biomedical laboratory will be stored in InLab (Clinical Laboratory Information Management System). Initiator™, Alphadas®, and InLab are validated and are Code of Federal Regulations (CFR) part 11 compliant applications.

Clinical data management will be performed in accordance with applicable Syneos standards and data cleaning procedures to ensure the integrity of the data, e.g., removing errors and inconsistencies in the data. Adverse events and concomitant medication terms will be coded using the Medical Dictionary for Regulatory Activities (MedDRA).

9.14 Subject Withdrawal and Replacement

Subjects will be advised that they are free to withdraw from the study at any time. Over the course of the study, the Sponsor and the Investigator or a Sub-investigator may withdraw any subject from the study for one of the reasons described below; subject withdrawal will be done in accordance with the clinical site's SOP:

- safety reason;
- non-compliance with protocol requirements;
- significant protocol deviation;
- positive alcohol breath test, cotinine test, drug screen, or pregnancy test;
- vomiting within 4 hours after dosing;
- marked prolongation of the QT/QTc interval (increases in QT/QTc to >500 ms or of >60 ms over baseline);
- unblinding of subjects treatment

Hematology, biochemistry, coagulation (PT and PTT), and urinalysis results will be reviewed by an Investigator or Sub-investigator prior to dosing, subjects will be withdrawn from the study if it is deemed that the subject's safety may be at risk on the basis of these test results.

Subjects excluded from dosing in one period as per criteria listed above, may be invited to participate in subsequent periods of the study if deemed appropriate by the Investigator and appropriate from a statistical standpoint (i.e. would permit adequate statistical comparison). However, subjects with positive alcohol, cotinine, drug screen, or pregnancy test and subjects withdrawn due to unblinding of the study treatment, will be definitively withdrawn from the study.

Subjects who withdraw or are withdrawn from the study after dosing will not be replaced. However, in the event that the number of drop-outs exceeds initial expectations, subjects who withdraw or are withdrawn might be replaced at the discretion of the Sponsor. Such replacement resulting in dosing more subjects than planned in this protocol would be documented in a protocol amendment.

Subjects who withdraw or are withdrawn will be asked to remain at the clinic until the Investigator or Sub-investigator agrees that the subject is fine and can be discharged. As soon as subject withdrawal is confirmed, blood sampling will be stopped. A PK blood draw may be collected at the time of withdrawal if deemed required by the Investigator. Study exit procedures/early termination visit will be performed at the time of withdrawal from the study or as soon as possible thereafter.

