9.4.1 Study Treatments T, ST, P and M

Therapeutic dose (T) of ITF2357 100 mg: administered as 1 x 10 mL of ITF2357 10 mg/mL oral suspension + 2 x 10 mL of matching placebo oral suspension (same appearance and taste as ITF2357) under fasting conditions (30 mL in total, for a total ITF2357 dose of 100 mg).

- Supratherapeutic dose (ST) of ITF2357 300 mg: administered as 3 x 10 mL of ITF2357 10 mg/mL oral suspension under fasting conditions (30 mL in total, for a total ITF2357 dose of 300 mg).
- Placebo (P): administered as 3 x 10 mL of matching placebo oral suspension (same appearance and taste of ITF2357) administered under fasting conditions (30 mL in total).

Sponsor, subjects, Investigators, the clinical personnel involved in the collection, monitoring, revision, or evaluation of adverse events, or personnel who could have an impact on the outcome of the study will be blinded with respect to the subject's treatment assignment (ITF2357 [T and ST]) and placebo [P]). Blinding will be maintained until the study has been finalized, the database has been verified, and all protocol violations have been determined. All personnel involved directly in the study shall be unaware of the treatment assigned to the subjects until the database has been closed. The ECG Central Core Laboratory's ECG Analyst, who is different from those who will evaluate laboratory assessments and AEs, will be blinded with respect to the subject's treatment assignment (including moxifloxacin arm), study period, time point of ECG recording and subject details.

The unblinded team at site will comprise the designated pharmacy personnel at the clinical site not directly involved with the clinical aspects of the trial who will prepare and dispense the study medication, will be aware of the randomization code. The study drug and placebo will have the same visual appearance in order to avoid compromising the study blinding.

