9.4.2 Study Treatment M

Study treatment M (moxifloxacin) is supplied as a tablet formulation while study treatments T, ST (therapeutic and supratherapeutic doses of ITF2357) and P (matching placebo) are supplied as oral suspension formulations. The positive control, study treatment M (moxifloxacin) will be

administered on an open label basis. The use of a double-blinded positive control is not mandatory, ⁶ provided that the reading of ECGs is performed in a blinded manner as described above

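### Marked QT/QTc prolongation is only a discretionary reason for withdrawal and is absent from the definitive withdrawals, so no rule bars further dosing after it.

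*Protocol*

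**What the plan says.** Protocol 9.14 states that the Sponsor and the Investigator or a Sub-investigator "may withdraw any subject from the study for one of the reasons described below". Seven reasons follow, one of them "marked prolongation of the QT/QTc interval (increases in QT/QTc to >500 ms or of >60 ms over baseline". Two later sentences deal with return:

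- "Subjects excluded from dosing in one period as per criteria listed above, may be invited to participate in subsequent periods of the study", provided that the Investigator finds it appropriate and that it is appropriate statistically.
- The exception: "subjects with positive alcohol, cotinine, drug screen, or pregnancy test and subjects withdrawn due to unblinding of the study treatment, will be definitively withdrawn".

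SAP 3.7 carries the same list and the same two sentences.

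On ECG review, Protocol 9.10 says "Safety parameters, including laboratory results and ECG, will be assessed by an Investigator or Sub-investigator", with the site's "ECG acceptance ranges as suggested guidelines in making the medical assessment". On blinding, Protocol 9.4.1 keeps "Sponsor, subjects, Investigators, the clinical personnel involved in the collection, monitoring, revision, or evaluation of adverse events" unaware of whether T, ST or P was given. Moxifloxacin is "administered on an open label basis" (Protocol 9.4.2).

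**The concern.** This study is run to find out whether ITF2357 prolongs QTc. It doses healthy volunteers at 100 mg and 300 mg and includes a positive control that Protocol 5.2 describes as prolonging QTc. The sponsor has set its own thresholds for marked prolongation, but crossing them leads to no required action. A positive cotinine test always ends participation; a QTc above 500 ms does not.

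What is at stake is participant safety. As the text stands, a volunteer with marked prolongation on 100 mg could be given 300 mg or moxifloxacin in a later period, on a judgement made without knowing what caused the event or whether the next suspension dose is 300 mg.

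**Working it through.** **Step 1: which withdrawal reasons are final.** The seven reasons in Protocol 9.14, set against the definitive-withdrawal sentence:

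| Reason | Definitive? |
|---|---|
| Safety reason | No |
| Non-compliance | No |
| Significant protocol deviation | No |
| Positive alcohol, cotinine, drug or pregnancy test | Yes |
| Vomiting within 4 hours of dosing | No |
| Marked QT/QTc prolongation | No |
| Unblinding | Yes |

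**Step 2: does the return clause reach a QT event?** It speaks of subjects kept from dosing in one period, which suggests a decision before the dose. QT prolongation would usually be seen after it. But the clause points back to the whole list, which holds another post-dose event (vomiting). Two readings follow:

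- *Broad:* the clause covers QT prolongation, and the subject may be invited back.
- *Narrow:* the clause covers pre-dose exclusions only. Withdrawal for QT prolongation is still optional, so the subject can simply continue.

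Neither reading contains a mandatory stop.

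**Step 3: is there a stop elsewhere?**

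- Protocol 9.4.1 makes unblinding final, and Protocol 9.16 does the same for pregnancy.
- The mandatory pre-dose review in Protocol 9.14 concerns laboratory results, not ECGs.
- The QTcF >450 msec exclusion (Protocol 8.3, criterion 3) applies at screening.
- Eligibility is reviewed in Period 1 only (Protocol 9.2.1).
- Protocol 9.10 leaves ECG findings to medical judgement.

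**Step 4: what could still be given.** Counted from the sequence table in Protocol 9.4:

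| Event on | Still to come | Sequences | Count |
|---|---|---|---|
| T | ST or M | 1, 3, 5, 7, 8, 9, 10 | 7/12 |
| ST | M | 1, 2, 5, 7, 9, 11 | 6/12 |
| M | ST | 3, 4, 6, 8, 10, 12 | 6/12 |

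In total, 7 + 6 + 6 = 19 of 36 combinations of sequence and active treatment. In 7 + 6 = 13 of them the event falls on blinded T or ST; in 6 it falls on open-label M. In sequences 1, 7 and 9 (3 of 12), 300 mg is the very next dose after 100 mg.

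**Step 5: what a definitive stop would cost in data.** Each of T, ST and M appears three times in each period. The mean number of periods remaining after an event is therefore (3 + 2 + 1 + 0)/4 = 1.5. At least one of T, ST and M is still to come in 7 cells after T, 9 after ST and 8 after M: 7 + 9 + 8 = 24 of 36. Those subjects would leave the PK Population, which requires all three treatments (Protocol 12.3.3). The figure is a minimum, because the period of the event may itself be left incomplete. The PK/QTc Population needs only one post-dose pair of concentration and QTcF (Protocol 12.3.5), so data already collected remain eligible for the primary analysis.

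**The case against.** The best reply has four parts.

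*The return clause may not apply.* It follows directly after the paragraph on pre-dose laboratory review, and a subject withdrawn from the study goes through exit procedures. This stands as far as it goes: the clause is ambiguous for post-dose events. A reader might infer that the protocol plainly allows these subjects to be re-invited, or even expects it. The documents do not support that. Return is at most permitted, and it needs both the Investigator's agreement and statistical appropriateness. The second condition is not a safety check.

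*Safeguards exist.* There is a separate ground for safety reasons, and the Sponsor may also withdraw a subject. Safety ECGs are taken pre-dose and at 2, 3, 6, 12 and 24 hours in every period. An Investigator is on site until 4 hours post-dose, subjects are confined to 72 hours, and the washout is at least 7 days. All of this is real, so it would be wrong to infer that such a subject is unprotected. But the ECGs and the confinement detect and manage an event; whether dosing continues remains a judgement. The site SOP that governs withdrawal is not in the documents and cannot be counted either way.

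*The cotinine comparison is unequal.* Positive substance tests breach an eligibility criterion, whereas QT prolongation needs interpretation, can occur on placebo, and is worded to include uncorrected QT. This is fair. It is a reason to define the trigger carefully, not to leave it optional.

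*The cell counts are not risks.* Correct. They follow from the sequence table and would be the same for any reason for withdrawal.

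**Conclusion.** The gap is real in this limited form: under Protocol 9.14 and SAP 3.7 marked QT/QTc prolongation never requires a subject to stop, whichever way the return clause is read. After an event on 100 mg, 300 mg or moxifloxacin is still ahead in 7 of 12 sequences. For T, ST and P the decision is made blind; for moxifloxacin the treatment is known.

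Two further inferences should be resisted. The first is that the risk is high: the documents give no figure from which the rate of such events on ITF2357, or of re-dosing after one, can be computed. The second is that the primary concentration-QTc result is at risk: no such effect is claimed, and the point does not depend on one.

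The conclusion rests on the public text and on the sequence table as printed. It would fall away if the site SOP already imposes a mandatory stop. It is best treated as a cheap improvement to participant safety.

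**What to change.** In Protocol 9.14 and SAP 3.7, add this group to the sentence on definitive withdrawal:

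*subjects with post-dose QTcF >500 ms or >60 ms above that period's pre-dose baseline on a safety ECG, taken as the mean of triplicate ECGs recorded immediately (within about 5 to 10 minutes) after the first reading, or on a centrally read ECG available before the next dosing.*

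The thresholds are the sponsor's own. QTcF is the measure that SAP 9.5 names for clinical evaluations, and averaging three ECGs follows the screening rule in Protocol 8.3. Immediate repeats guard against a spurious single reading without giving a transient peak long to resolve. The 5 to 10 minutes is a suggestion, not a figure from the documents. The central-reading limb is conditional because the documents do not say when those readings come back. Keep the present discretionary QT/QTc criterion for all other cases.

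The cost is a protocol amendment, which needs ethics committee approval because it is not merely logistical or administrative (Protocol 13.1), the matching SAP change, and repeat ECGs for each event. The affected subject loses the remaining periods (0 to 3, mean 1.5), possibly including that subject's own placebo period, and leaves the PK Population in at least 24 of 36 active-treatment cells. Subjects withdrawn after dosing are not normally replaced.
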